#### 4.1.1 Dose Escalation Phase

The goal of the Dose Escalation Phase of this study is to initially characterize the safety and tolerability of MGC018 administered alone or in combination with MGA012 and, more specifically, to define the MTD of these respective monotherapy and combination regimens. If no MTD is defined during the dose escalation of MGC018 monotherapy (Module A) after escalation to the maximum protocol-specified dose, then that dose level will be designated as the MAD for MGC018 monotherapy. Similarly, if no MTD is defined during dose escalation of the combination of MGC018 and MGA012 (Module B), after escalation to the maximum protocol-specified dose, then that dose level will be designated as the MAD for MGC018 and MGA012 combination therapy.

For the purposes of guiding decisions regarding dose escalation, the **DLT Evaluation Period** for Module A (monotherapy) will be 21 days following administration of the first dose of MGC018. For Module B (combination therapy), the DLT evaluation period will be 42 days in duration.

Dose escalation will follow a conventional 3+3+3 design: successive cohorts of 3 to 9 participants each will be evaluated in sequential escalating doses of MGC018 administered alone (Module A) or in combination with MGA012 (Module B) as shown below (**Table 3** and **Table 4**).

Sentinel dosing will be used for the first 2 dose levels. The first administration of MGC018 in participants in the first 2 dose levels in Module A will be staggered by at least 48 hours.

In Module B, MGA012 will be administered at a dose of 375 mg (flat dose) Q3W, beginning on Day 22 of Cycle 1, and continuing on Days 1 and 22 of every cycle thereafter.

Participants who require dose delays greater than 21 days secondary to AEs considered unrelated to study treatment or any other cause unrelated to study treatment are considered unevaluable for safety and toxicity during the DLT evaluation period and will be replaced.

Intermediate dose levels may be explored based on review of the cumulative safety data and upon agreement between the investigators and the sponsor.

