## 4.2 Dose Limiting Toxicity

For the purposes of guiding study decisions regarding dose escalation, DLTs will be based on study drug-related AEs or laboratory abnormalities that occur up to Study Day 21 of Cycle 1 in the Dose Escalation Phase only for Module A and Study Day 42 of Cycle 1 in the Dose Escalation Phase only for Module B. The severity of AEs will be graded according to the National Cancer Institute Common Terminology Criteria for Adverse Events version 4.03 (NCI CTCAE v4.03). Dose-limiting toxicities will be defined separately for hematologic, non-hematologic, and hepatic non-hematologic events.

In general, for participants who experience toxicity that may meet the criteria for a DLT, subsequent administration of the study drugs should be held pending management and/or resolution of the event and assessment of attribution to the study drug. Criteria for discontinuation of therapy are outlined in [Section 5.4](#).

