### 4.2.1 Hematologic Dose Limiting Toxicity

Hematologic DLT is defined as follows:

- Grade 4 neutropenia lasting > 7 days
- $\geq$  Grade 3 febrile neutropenia lasting > 48 hours or any  $\geq$  Grade 3 febrile neutropenia associated with hemodynamic compromise or objective evidence of infection
- Grade 4 thrombocytopenia, irrespective of duration
- Grade 3 thrombocytopenia associated with clinically significant bleeding
- $\geq$  Grade 3 hemolysis

The following events will be specifically **excluded** from the definition of hematologic DLT:

- $\geq$  Grade 3 lymphopenia
- Grade 3 anemia that is not associated with other clinically significant complications

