| CBC, PLTs, diff;
Chemistry Panel             | X                                                                                                                                                                                                                                                                                                                                                 | X       |              | X              |        | X               |                                | X                                            | X               |                                 |                 | X                                           |                    |
|                                                         | To be collected pre-infusion and prior to prophylactic pre-medications on dosing days. Day 1 laboratory blood samples can be collected up to 1 day before infusion. See Appendix 2 for list of assessments.                                                                                                                       |         |              |                |        |                 |                                |                                              |                 |                                 |                 |                                             |                    |
| PT or INR                                        | X                                                                                                                                                                                                                                                                                                                                                 | X       |              | X              |        | X               |                                | X                                            | X               |                                 |                 | X                                           |                    |

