| Survival Follow-up                                                                                                                                                                                                                                                                                                                                                                                                                                                                                |                                              |         |              |                |        |                 |                                |                                              |                 |                                 |                 |                                             | X                  |
| Survival follow-up collected every 3 months (90 days ± 7 days) by clinic visit, telephone, paper mail, or other electronic contact for 2 years; information regarding response status and/or the occurrence of disease progression may be collected approximately every 3 months in participants who discontinued from study treatment due to reasons other than progressive disease, if they have not initiated any other cancer directed therapy. See Section 9.17 for details. |                                              |         |              |                |        |                 |                                |                                              |                 |                                 |                 |                                             |                    |

- 1 The Screening visit should occur within 28 days prior to Day 1.
- 2 Cycle 1 Day 42 and Cycle 2 Day 1 may be combined. Regardless if the visits are combined or not, Cycle 1 Day 42 assessments should occur before Cycle 2 Day 1 assessments. The same applies to all consecutive cycles.
- 3 Evaluations/procedures performed on Days 23, 25, 29, and 36 apply to Cycle 2 only.
- 4 The EOTV should be performed within 30 days following the last dose of study drug.

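### Module B dose escalation has no mandatory blood count or chemistry between the first combination dose (Day 22, drawn pre-infusion) and Cycle 2 Day 1, so short-lived, silent laboratory DLTs may be missed

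*Protocol*

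**What the plan says.** **Window.** Protocol Section 4.1.1: "For Module B (combination therapy), the DLT evaluation period will be 42 days in duration". Section 4.2 counts DLTs up to "Study Day 42 of Cycle 1 in the Dose Escalation Phase only for Module B". SAP Section 3.1 repeats the 42 days and adds nothing on ascertainment.

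**First combination dose.** MGA012 starts on Day 22 of Cycle 1 (Sections 4.1.1 and 6.1).

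**Laboratory schedule.** In the Module B table of Appendix 1, the row "CBC, PLTs, diff; Chemistry Panel" is marked at screening, Cycle 1 Days 1, 8 and 22, Days 1 and 22 of later cycles, and the end-of-treatment visit. Cycle 1 Days 2 and 4, 15 and 42 are blank. The note under the row says "To be collected pre-infusion and prior to prophylactic pre-medications on dosing days" and "Day 1 laboratory blood samples can be collected up to 1 day before infusion". The table notes add "Cycle 1 Day 42 and Cycle 2 Day 1 may be combined" and "Evaluations/procedures performed on Days 23, 25, 29, and 36 apply to Cycle 2 only".

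**Laboratory DLTs.** Some count at any duration: Grade 4 thrombocytopenia (Section 4.2.1), and transaminases above 8 times or bilirubin above 5 times the upper limit of normal (Section 4.2.3). Others need a time course: "Grade 4 neutropenia lasting > 7 days", and Grade 3 transaminase or bilirubin elevations that fail to improve by 7 and 14 days.

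**The concern.** The definitions in Section 4.2 assume laboratory values that the schedule does not require. The Day 22 sample is taken before MGA012 is given, so it says nothing about the combination. The only scheduled sample that does comes about three weeks later, at the edge of the window. A platelet count that falls to Grade 4 and recovers between those dates meets the DLT definition but leaves no scheduled record. Nor can one sample show that neutropenia lasted more than 7 days, or that a liver elevation failed to improve by set dates.

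The DLT rate and MTD of the combination are part of the primary objective (Section 3.1). A missed laboratory DLT biases the observed rate downward in cohorts of 3 to 9, where a single event can change the decision.

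**Working it through.** **Reading the row.** Tables in a PDF can shift. Here the CBC and chemistry marks line up with the dosing rows (MGC018 on Days 1 and 22) and with the vital-signs row, which carries Day 8 as a non-dosing visit. The reading is secure.

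**Day count.** Days 22 to 42 inclusive: 42 − 22 + 1 = 21 days, and 21/42 = 50% of the window. From Day 22 to nominal Cycle 2 Day 1: 43 − 22 = 21 days. Cycle 2 Day 1 has a window of ±1 day and its sample may be taken a day early, so the draw lies between Day 41 and Day 44.

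**Chance that the one scheduled draw sees an episode.** Assume onset is uniform over the 21 days and the abnormality lasts d days. A draw at Day 43 sees it if onset falls in the last d days, so the share is d/21 for d up to 21. Adding draws on Days 29 and 36 gives 3d/21 for d up to 7.

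| d (days) | Scheduled draw only | Plus Days 29 and 36 |
|---|---|---|
| 3 | 3/21 = 14% | 9/21 = 43% |
| 5 | 5/21 = 24% | 15/21 = 71% |
| 7 | 7/21 = 33% | 21/21 = 100% |
| 10 | 10/21 = 48% | 100% |
| 11 | 11/21 = 52% | 100% |
| 14 | 14/21 = 67% | 100% |

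A draw on Day 41 or 42 leaves the first column unchanged. At Day 44 the share is (d − 1)/21: 10%, 19%, 29%, 43%, 48% and 62%. The table is generous to the plan, because it counts an abnormality first seen on Day 43 as a detected DLT although its onset cannot be dated to Day 42 or before.

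**Whole-day check, 5-day episode, onset on Days 23 to 42 (20 days).** A draw on Day 43 sees onsets on Days 39 to 42: 4/20 = 20%. A draw on Day 42 sees Days 38 to 42: 5/20 = 25%. Days 29 and 42: 10/20 = 50%. Days 29, 36 and 42: 15/20 = 75%.

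**Sensitivity to onset.** If onset falls one to two weeks after the combination dose (Days 29 to 36), the Day 43 draw sees none of the 5- or 7-day episodes. From 7 to 14 days the share is (d − 7)/7: 14% at 8 days, 43% at 10 and 100% at 14.

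**Monotherapy half.** With draws on Days 8 and 22, a 5-day episode with onset on Days 2 to 21 is seen for onsets on Days 4–8 and 18–21: 9/20 = 45%. Adding Day 15 adds onsets on Days 11–15: 14/20 = 70%.

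**Duration criteria.** Take an 8-day episode, the shortest whole-day length above 7 days, with draws on Days 29, 36 and 42. Two draws fall inside it only for onset on Days 29, 35 or 36: 3/20 = 15%. Those pairs are 6 or 7 days apart, so they do not by themselves show more than 7 days.

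I do not carry these shares into an escalation probability. The documents do not say what fraction of DLTs would be laboratory-only, short and silent.

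**The case against.** **Other provisions generate tests.** Section 7.4 asks investigators to consider weekly or bi-weekly counts and calls for counts on fever or evidence of infection. Sections 7.4.1 and 7.4.2 specify weekly counts once higher-grade neutropenia or thrombocytopenia is found. Section 7.2.2 specifies liver tests at least twice weekly for Grade 3 elevations. Table 6 suggests weekly laboratory tests as indicated for other toxicities, and Section 4.6 allows extra local tests. This largely stands, and it limits the problem to short, asymptomatic abnormalities with no trigger. It does not close the gap: each provision is optional or starts from a symptom or a known abnormality, and the Section 7.4 monitoring covers blood counts, not chemistry.

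**The Cycle 2 Day 1 draw can fall inside the window.** True, so it would be wrong to say that nothing can be sampled by Day 42. Moving the draw by a day hardly changes what it sees (20% against 25% for 5-day episodes).

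**Later data still inform escalation.** Section 4.3 has the medical monitor, the Independent Safety Monitor and the investigators weigh data from beyond the DLT period, and Section 9.8 requires laboratory review before every MGC018 infusion. Table 4 also plans no MGC018 dose above the monotherapy MTD. These safeguards stand for abnormalities that persist or recur. They cannot recover one that came and went unsampled.

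**Extra draws alone do not prove duration.** Correct, as the 15% figure shows. Repeat testing therefore has to be part of the fix.

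**Conclusion.** The point holds in limited form. No mandatory CBC or chemistry falls between the pre-infusion Day 22 sample and Cycle 2 Day 1, and the schedule and the DLT definitions do not fit each other. Short-lived, asymptomatic laboratory DLTs of the combination may be missed unless a discretionary or triggered test is done. Under uniform onset, the scheduled draw alone sees about 14% of 3-day, 24% of 5-day, 33% of 7-day, 48% of 10-day and 67% of 14-day episodes. Onset pattern and duration are both assumptions.

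A reader might infer two stronger things. One is that most laboratory DLTs in the combination half would go unseen. That holds only for episodes of about 10 days or less and only if no unscheduled test is done; at 11 days the scheduled draw sees 52%, and the documents give no durations. The other is that escalation would proceed past toxic doses. The documents do not establish that, given the review of later data, the pre-dose laboratory check and the planned ceiling in Table 4. What they support is a risk of under-ascertainment in a primary endpoint.

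**What to change.** Reconcile the Module B Cycle 1 laboratory rows in Appendix 1 with the DLT definitions in Section 4.2, for dose escalation:

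- Add CBC and chemistry to Day 15, where Appendix 3 (Table 14) already has a blood draw. Assumed 5-day episodes in the first half go from 45% to 70% seen.
- Schedule local CBC and chemistry between Day 22 and Day 42. Weekly draws are one example and raise 5-day detection to about 71–75%. The gain comes from draws inside the interval; a Day 42 draw alone adds little.
- State that an abnormal value which could meet a duration-based DLT is repeated at intervals short enough to show whether the 7-day or 14-day criterion was met.
- State how an abnormality first found on Cycle 2 Day 1 is classified when its onset cannot be dated to the window.

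The sponsor should choose the exact days. The Day 29 and 36 visits now exist only in Cycle 2, so the Cycle 1 draws would be new. On the planned maximum of 27 escalation participants, two extra draws each is 2 × 27 = 54 local draws, plus added tests on an existing draw, any repeat tests and a schedule amendment.

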**Module B Dose Escalation and Cohort Expansion Phases**

| EVALUATION/
PROCEDURE                                                                                                                                                                                                                                                                                                                                                                                                                                                                          | Screening 
(Within 28 days) | Cycle 1 |              |                |        |                 |                                | Cycle 2 and subsequent Cycles  |                 |                                 |                 | End of
Treatment
Visit  | Post
TRT
FUP |
|---------------------------------------------------------------------------------------------------------------------------------------------------------------------------------------------------------------------------------------------------------------------------------------------------------------------------------------------------------------------------------------------------------------------------------------------------------------------------------------------------|----------------------------------------------|---------|--------------|----------------|--------|-----------------|--------------------------------|----------------------------------------------|-----------------|---------------------------------|-----------------|---------------------------------------------|--------------------|
|                                                                                                                                                                                                                                                                                                                                                                                                                                                                                                   |                                              | Day 1   | Days 2 and 4 | Day 8
(±1d) | Day 15 | Day 22
(±1d) | Day 42 
(±3d) | Day 1
(±1d)                               | Day 22
(±1d) | Days 23, 25,
29, 36
(±1d) | Day 42
(±3d) |                                             |                    |
| Tumor Assessment
(CT/PET/MRI)                                                                                                                                                                                                                                                                                                                                                                                                                                                                  | X                                            |         |              |                |        |                 | X                              |                                              |                 |                                 | X               | X                                           |                    |
| Radiographic disease assessments will occur on Day 42 ± 3 days for the first four cycles, and every other cycle thereafter. Assessment will also be done at EOTV.                                                                                                                                                                                                                                                                                                                                 |                                              |         |              |                |        |                 |                                |                                              |                 |                                 |                 |                                             |                    |
| Survival Follow-up                                                                                                                                                                                                                                                                                                                                                                                                                                                                                |                                              |         |              |                |        |                 |                                |                                              |                 |                                 |                 |                                             | X                  |
| Survival follow-up collected every 3 months (90 days ± 7 days) by clinic visit, telephone, paper mail, or other electronic contact for 2 years; information regarding response status and/or the occurrence of disease progression may be collected approximately every 3 months in participants who discontinued from study treatment due to reasons other than progressive disease, if they have not initiated any other cancer directed therapy. See Section 9.17 for details. |                                              |         |              |                |        |                 |                                |                                              |                 |                                 |                 |                                             |                    |

- 1 The Screening visit should occur within 28 days prior to Day 1.
- 2 Cycle 1 Day 42 and Cycle 2 Day 1 may be combined. Regardless if the visits are combined or not, Cycle 1 Day 42 assessments should occur before Cycle 2 Day 1 assessments. The same applies to all consecutive cycles.
- 3 Evaluations/procedures performed on Days 23, 25, 29, and 36 apply to Cycle 2 only.
- 4 The EOTV should be performed within 30 days following the last dose of study drug.

Abbreviations: ADA = anti-drug antibody; AE = adverse event; CBC = complete blood count; CT = computed tomography; diff = differential; ECG = electrocardiography; ECOG PS = Eastern Cooperative Oncology Group Performance Status; EOI = end of infusion; EOTV = End of Treatment Visit; FUP = follow-up; INR = international normalized ratio; mCRPC = metastatic castration-resistant prostate carcinoma; MRI = magnetic resonance imaging; MUGA = multigated acquisition (scan); PET = positron emission tomography; PLTs = platelets; PSA = prostate-specific antigen; PT = prothrombin time; SAE = serious adverse event; SSE = symptomatic skeletal event; TCR = T-cell repertoire; TRT = treatment; TSH = thyroid stimulating hormone.

